8.9 Concomitant Medication of Interest

Concomitant medications of interest are all anti-infectives which are administered after the reported start date of Revcovi in the CLI-06814AA1-01 Study, regardless of when they were started. All concomitant medications will be coded using the WHO Drug, Version 2020 Q1 or most recent version prior to database lock. The frequency of concomitant medications

Chiesi Farmaceutici S.p.A. Statistical Analysis Plan CLI-06814AA1-01 Version 4.0 06June2023

will be summarized using descriptive statistics by therapeutic class (ATC level 2) and preferred term. Subjects are counted only once in each therapeutic class category, and only once in each preferred term category.

9. QUALITY OF LIFE ANALYSIS

The following quality of life (QoL) questionnaires will be administered prior and during the treatment with Revcovi: PedsQL scales for subjects aged 1 to 12 months (infants), 13 to 24 months (infants), 2 to 4 years (toddlers), 5 to 7 years (young children), 8 to 12 years (children), and 13 to 18 years (teens); for subjects over 18 years, the SF-36 questionnaire and the PADQoL-16 will be administered at the following time points:

Baseline (prior to first dose of Revcovi)

3-months

6 months

9 months

12 months

18 months

24 months

A data review revealed that only few QoL data has been captured during the study. Therefore, QoL data collected will only be listed but not summarized.

Changes for QoL data will only be summarized for Adagen naïve and Adagen transitioning patients.

PedsQL

The PedsQL will be scored² to the 4 scales physical functioning, emotional functioning, social functioning, and school functioning. For children 1-12 months and 13 to 24 months, the school functioning scale is replaced by the cognitive functioning scale. Two summary scores (total score and psychological health summary score) will also be calculated and analyzed. All scales will be transformed to a scale from 0 to 100 where 100 is the best possible value. The actual values and the changes from baseline will be listed for all analysis time points.

SF-36 Version 1.0

The SF 36-questionnaire is a 36-item questionnaire which will be condensed to 8 scores (physical functioning, role-physical, bodily pain, general health, vitality, social functioning, role-emotional, and mental health). All scores will be normalized to a scale from 0 to 100.

PADQoL-16

The PADQoL-16 will be scored to 7 subscores (general health, vitality, physical functioning, role (physical), role (emotional), mental health, social functioning) and one total score. The exact scoring algorithm is summarized in Appendix B. All scales will be standardized to a range from 0 to 100. The actual values and their changes from baseline will be listed for all analysis time points.

10. INTERIM ANALYSES

An interim analysis was be performed 24 months after the first subject is enrolled. The following data has been presented in the interim analysis:

- Subject disposition
- Demography and other baseline characteristics
- Administration of Revcovi (until the data cut date)
- Biochemical assessments of trough plasma dAXP and ADA activity
- Prior ERT treatment
- Lymphocytes subsets
- Quantitative immunoglobulin
- Hospitalizations and infections
- Adverse events

11. PHARMACOKINETIC ANALYSIS

N/A.

12. STATISTICAL SOFTWARE

All data listings, summaries, and statistical analyses will be generated using SAS[®] Version 9.4 or higher.

13. RULES AND DEFINITIONS

13.1 Timing of Analyses

One interim analysis has been performed approximately 24 months after the first subject was enrolled in the registry. The final analysis will be performed after database lock.

13.2 Assignment of Study Days

For the purposes of data listings and summaries, "Study Day" will be calculated relative to the reported first dose of Revcovi, which is for the STP2270-002 patients, the reported date of the first dose of Revcovi in the STP-2279-002 study (i.e., date of interest – reported date of first dose of Revcovi). One day will be added if this difference is ≥ 0 , so that the first dose of study medication is considered "Study Day 1." The day prior to the first dose of study medication is considered "Study Day -1". For analysis purposes, there will be no "Study Day 0".

13.3 Baseline and Assignment to Suggested Study Visits

For Adagen-naïve patients and Adagen-transitioning patients, baseline will be defined as the last measurement for a variable with a non-missing value prior or on the treatment start date with Revcovi in this study (CLI-06814AA1-01). For STP 2279-002 subjects, the baseline will be defined as the last measurement for a variable with a non-missing value prior or on the treatment start date with Revcovi in STP 2279-002. At Study Day 1, it is assumed that all assessments are performed prior to the application of the first dose of Revcovi. However, adverse events with the same onset date as the start date of Revcovi will be assumed to be post-treatment and counted as treatment-emergent AEs.

Assessments will be 'slotted' to the treatment visits as described below. Reference date for all visits will be the start date of Revcovi (Study Day 1). Study Day 1 for the subjects transitioning from the STP-2279-002 study will be the reported start date of Revcovi in the STP-2279-002 study. Depending on the subject status (Adagen-Naïve subject or Adagen transitioning subject), the suggested visit schedule is different for the first 9 treatment months. For the Adagen-Naïve subjects, there are more suggested visits compared to the Adagen transitioning subjects. Participants of the STP 2279-002 study will be analyzed according to the Schedule of Assessments for Adagen-Transitioning Subjects. The visit windows will be defined for all assessments as follows:

Suggested Visit	Targeted Study Day	Visit window (Study Day)					
Enrollment/Baseline	Last available data	$-\infty$ to 1					
	prior or at Study Day 1						
TW 4	30	2-45					
TW 8	60	46-75					

Adagen-Transitioning subjects

Chiesi Farmaceutici S.p.A. Statistical Analysis Plan CLI-06814AA1-01 Version 4.0 06June2023

TM 6 TM 9 TM 12	182 273	137-227 228-319
		228-310
TM 12		
	365	320-410
TM 15	456	411-501
TM 18	547	502-592
TM 21	638	593-684
TM 24	730	685-776
TM 27	822	777-867
TM 30	913	868-958
TM 33	1004	959-1049
TM 36	1095	1050-1141
TM 39	1187	1142-1232
TM 42	1278	1233-1324
TM 45	1370	1325-1415
TM 48	1461	1416-1506
TM 51	1552	1507-1597
TM 54	1643	1598-1689
TM 57	1735	1690-1780
TM 60	1826	1781-1871
TM 63	1917	1872-1962
TM 66	2008	1963-2055
TM 69	2100	2056-2145
TM 72	2191	2146-2236
TM 75	2282	2237-2328
TM 78	2374	2329-2419
TM 81	2465	2420-2510
TM 84	2556	2511-2601
TM 87	2647	2602-2693
TM 90	2739	2694-2784
TM 93	2830	2785-2875
TM 96	2921	2876-2966
TM 99	3012	2967-3057
TM 102	3103	3058-3148
TM 105	3194	3149-3240
TM 108	3286	3241 or later
1-month post-	30	1-60
transplantation*		

6-month post-	182	61 onwards
transplanation*		

*Reference date for the 1- and 6-month post-transplantation visit is the date of the last dose of REVCOVI

Suggested Visit	Targeted Study day	Visit window
Enrollment/Baseline	Last available data	-∞ - 1
	prior or at Study Day 1	
TW 2	15	1-22
TW 4	30	23-37
TW 6	45	38-52
TW 8	60	53-67
TW 10	75	68-83
TW 12	91	84-106
TM 4	121	107-136
TM 5	151	137-166
TM 6	182	167-197
TM 7	212	198-227
TM 8	242	228-257
TM 9	273	258-319
TM 12	365	320-410
TM 15	456	411-501
TM 18	547	502-592
TM 21	638	593-684
TM 24	730	685-776
TM 27	822	777-867
TM 30	913	868-958
TM 33	1004	959-1049
TM 36	1095	1050-1141
TM 39	1187	1142-1232
TM 42	1278	1233-1324
TM 45	1370	1325-1415
TM 48	1461	1416-1506
TM 51	1552	1507-1597
TM 54	1643	1598-1689
TM 57	1735	1690-1780
TM 60	1826	1781-1871
TM 63	1917	1872-1962
TM 66	2008	1963-2055

Adagen-Naïve Subjects

6-month post- transplanation*	182	61onwards
1-month post- transplantation*	30	1-60
TM 108	3286	3241 or later
TM 105	3194	3149-3240
TM 102	3103	3058-3148
TM 99	3012	2967-3057
TM 96	2921	2876-2966
TM 93	2830	2785-2875
TM 90	2739	2694 or later
TM 87	2647	2602-2693
TM 84	2556	2511-2601
TM 81	2465	2420-2510
TM 78	2374	2329-2419
TM 75	2282	2237-2328
TM 72	2191	2146-2236
TM 69	2100	2056-2145

*Reference date for the 1- and 6-month post-transplantation visit is the date of the last dose of REVCOVI

For by-visit summaries, if there are multiple assessments in the specified time windows, the value most closely to the targeted time point will be used for the analysis. If 2 timepoints have the same distance from the targeted time point, the value after the targeted timepoint will be used for the analysis.

Missing data will not be imputed.

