3.2 Sample Size and Power Considerations

No formal sample size is calculated for this study. This registry study will enroll all eligible subjects over a minimum of 2 years.

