5. GENERAL ANALYSIS CONSIDERATIONS

All analysis will be descriptive and no statistical hypothesis will be tested. Descriptive statistics for continuous variables will include number of observations (n), mean, standard deviation (SD), median, minimum (min), and maximum (max); for categorial variables counts and percentages for each category. Ninety-five percent confidence intervals (CIs) will be calculated for the main outcome variables without adjustment for multiplicity to generalize the results to the general population. If not otherwise noted, confidence intervals for continuous variables will be based on normal distribution, for categorial variables on Clopper-Pearson (Clopper and Pearson 1934). Confidence intervals for Poisson distributions will be calculated by the method of Ulm (Ulm 1990).

Time to event analyses will be performed by the Kaplan-Meier method (Kaplan and Meier 1958). Confidence intervals for the median survival time will be calculated based on the method of Brookmeyer and Crowley (Brookmeyer and Crowley 1982) after log-log transformation.

All analyses will be performed by subject status (Adagen-Naïve subject, Adagen-Transitioning subject, or STP-2279-002 participant) and overall. Subject status is as collected on the Adagen/Revcovi Treatment page in the eCRF. There is a different recommended visit schema for the Adagen naïve subjects and the Adagen transitioning subjects (Table 1 and Table 2). However, a data review revealed that the timing of the assessments is not following the suggested visit schema. Therefore, the slotting schema within each subject status will be uniform for all assessments. All assessments will be slotted to the closest visit suggested for the Adagen transitioning or Adagen naïve subjects, respectively, regardless of whether or not the specific assessment is recommended for this visit, Participants of the STP 2279-002 study will be analyzed per the Suggested Schedule of Assessments for Adagen-Transitioning Subjects. Therefore, the visit windows will be specific for each type of subjects (see Section 13.3). All visits will be included in the overall column, regardless of whether or not the specific visit is analyzed for all type of subjects.

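### In SAP 13.3 the Adagen-naïve window table counts Study Day 1 in both Baseline and TW 2, and leaves TM 90 open-ended across TM 93 to TM 108

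*SAP*

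**What the plan says.** SAP 13.3 gives one window table for Adagen-transitioning subjects, which also serves former STP-2279-002 participants, and one for Adagen-naïve subjects. The windows apply to all assessments.

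- **Day 1.** Baseline is the last non-missing value on or before the treatment start date, and "At Study Day 1, it is assumed that all assessments are performed prior to the application of the first dose of Revcovi". In the naïve table Baseline ends at Day 1 and TW 2 (target Day 15) is 1-22. In the transitioning table the first post-baseline window, TW 4, is 2-45.
- **TM 90.** The naïve row reads "TM 90 2739 2694 or later". The rows after it in the same table have their own windows, from "TM 93 2830 2785-2875" through "TM 108 3286 3241 or later". The transitioning row reads "TM 90 2739 2694-2784".
- **Slotting.** SAP 5 states: "All assessments will be slotted to the closest visit suggested for the Adagen transitioning or Adagen naïve subjects, respectively". It adds that this holds whether or not the assessment is recommended at that visit.
- **Several values in one window.** SAP 13.3 states: "if there are multiple assessments in the specified time windows, the value most closely to the targeted time point will be used for the analysis". Ties go to the later value, and missing data are not imputed.

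SAP 7.2.1 and 7.2.2 call for means and changes from baseline with 95% confidence intervals at every time point, for ADA activity, dAXP, lymphocyte subsets and immunoglobulins.

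**The concern.** Visit windows should give each study day to one visit only. The naïve table breaks this in two places.

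The Day 1 overlap matters more. It lets an untreated measurement serve as the first on-treatment result. The subject then contributes a pre-treatment level to the TW 2 mean and a zero to the TW 2 mean change. For ADA activity and dAXP the same value would also enter the percentage of subjects meeting the target level. Naïve subjects are the group started de novo on Revcovi, whose safety and efficacy the protocol sets out to describe (Protocol 6.1).

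The TM 90 row makes every assessment from Day 2785 onward eligible for two visits, against the SAP's own closest-visit rule.

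**Working it through.** **Inputs.** Windows and targets are from SAP 13.3. Visit content is from Protocol Appendix 2 and SAP Table 2. There is no sample-size figure to reproduce ("No formal sample size is calculated for this study").

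**1. How the plan sets its boundaries.** They are midpoints of adjacent targets.

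- TW 2/TW 4: (15 + 30)/2 = 22.5, giving 22/23 as stated.
- TW 10/TW 12: (75 + 91)/2 = 83, giving 83/84 as stated.
- TM 87/TM 90: (2647 + 2739)/2 = 2693, giving 2693/2694 as stated.
- TM 90/TM 93: (2739 + 2830)/2 = 2784.5, giving 2784/2785. The transitioning table states this; the naïve table does not.

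The only other departure in the naïve table is TM 66/TM 69. It ends at 2055 against a midpoint of (2008 + 2100)/2 = 2054. Both tables share it, and it creates no overlap.

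**2. Overlap check.** Windows [a, b] and [c, d] overlap if max(a, c) ≤ min(b, d).

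| Pair | max of starts | min of ends | Overlap |
|---|---|---|---|
| Naïve Baseline, TW 2 | 1 | 1 | Day 1 |
| Transitioning Baseline, TW 4 | 2 | 1 | none |
| Naïve TM 90, TM 93 | 2785 | 2875 | 2785-2875 |
| Naïve TM 90, TM 96 | 2876 | 2966 | 2876-2966 |
| Naïve TM 90, TM 99 | 2967 | 3057 | 2967-3057 |
| Naïve TM 90, TM 102 | 3058 | 3148 | 3058-3148 |
| Naïve TM 90, TM 105 | 3149 | 3240 | 3149-3240 |
| Naïve TM 90, TM 108 | 3241 | none | 3241 onward |

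Among the 46 naïve rows counted from first dose (Baseline plus 45 visits) there are no other overlaps. With TW 2 = 2-22 and TM 90 = 2694-2784 there are none at all.

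**3. When a Day 1 value becomes the TW 2 value.** Day 1 is 15 − 1 = 14 days from target. Day 2 is 13 days away and Day 22 is 7. Any sample in Days 2-22 is closer and displaces Day 1, so Day 1 is used only when that interval is empty.

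- *Subsets and immunoglobulins* are scheduled for naïve subjects at enrollment and TW 4, not at TW 2. A TW 4 visit within ±3 days falls on Days 25-31 if Week 4 is Day 28, or 26-32 if Day 29. Both ranges lie inside the TW 4 window (23-37). An adherent subject therefore has nothing in Days 2-22. If the baseline sample was drawn on Day 1 itself, that value fills TW 2.
- *ADA activity and dAXP* are scheduled at TW 2, so Day 1 is used only if that sample is missing or falls outside Days 2-22.

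**4. Effect on the summary.** If the Day 1 value is both baseline and TW 2, the change is x − x = 0. If k of the n subjects with a TW 2 value are of this kind, the reported mean change is (n − k)/n times the mean change in the rest. If k = n, which is possible for an assessment not scheduled at TW 2, the reported change is 0 with SD 0 and a confidence interval of zero width. The documents give neither n nor k.

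**5. When TM 90 goes wrong.** Day 2785 is 2785/365.25 = 7.6 years. Days 2694 and 2784 are each 45 days from target 2739, and Day 2785 is 46. If a record may serve two visits, a later value enters TM 90 only when Days 2694-2784 are empty; it then appears at TM 90 and again at its proper visit. If a program instead gives each record to the first matching row, everything from Day 2785 goes to TM 90 and TM 93 to TM 108 are empty.

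**The case against.** The case for leaving this alone is that the text already settles both points. Day 1 is declared pre-dose, the nearest-value rule drops Day 1 whenever a later sample exists, and the closest-visit rule in SAP 5 sends Day 2785 onward to TM 93 or later. Nothing is tested, and SAP 7 lists all efficacy data. On timing, Protocol 5 puts approval in October 2017. If naïve subjects started no earlier, Day 2785 falls no earlier than about mid-May 2025, almost two years after the June 2023 SAP.

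Most of this stands as a limit on size. It does not remove the errors. The pre-dose statement defines baseline but does not bar the same value from the TW 2 window. The nearest-value rule cannot help when the window is otherwise empty, which for subsets and immunoglobulins is the scheduled situation. Where a printed window and a general rule disagree, the SAP does not say which governs.

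A reader might also infer that the table wrongly sends compliant Week 12 visits to TW 10. The documents do not support that. The 83/84 boundary is the correct midpoint of the SAP's own targets, and Day 91 fits the 3-month time point in SAP 9. Only early visits are affected: Days 82-83 if Week 12 is Day 85, or Days 81-83 if it is Day 84. On-time and late visits go to TW 12. These are 2 or 3 of 7 calendar days, not a share of visits. The schedule's notes say it is not binding, and SAP 5 reports that actual timing departs from it.

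**Conclusion.** Two rows of the Adagen-naïve table are wrong as written.

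**TW 2** is the one with practical effect. It can report an untreated value as on-treatment, with change exactly 0, even for an adherent subject. This requires a sample drawn on Day 1 and none in Days 2-22. How many naïve subjects meet that condition is not in the documents. The effect is confined to TW 2 by-visit summaries and to the overall column that includes them.

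**TM 90** is an internal contradiction with no effect unless a naïve subject has data after Day 2784. The documents do not say whether any will. Former STP-2279-002 participants, whose Study Day 1 dates from that earlier study, use the transitioning table and are not touched.

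The slotting of early Week 12 visits is a side effect of the chosen targets. It is not an error and needs no change.

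**What to change.** In the naïve table of SAP 13.3:

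- set TW 2 to Days 2-22;
- set TM 90 to Days 2694-2784.

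Both follow the transitioning table. It would help to add a sentence saying that a Day 1 assessment is used only as baseline (adverse events keep their own rule). The cost is two cells and a matching program check before the final analysis, which follows database lock (SAP 13.1). The interim analysis included lymphocyte subsets and immunoglobulins (SAP 10). If it used these windows, check whether any naïve TW 2 value there carries a Day 1 date.

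Optionally, note in the SAP that Week 12 visits made one to three days early may be slotted to TW 10 and, if Week 10 is Day 70, that a visit on Day 67 goes to TW 8. Re-targeting the week visits is not required and has costs. For naïve subjects alone, targets of Days 29 and 57 for TW 4 and TW 8 would no longer match the transitioning targets of 30 and 60, although the overall column pools both groups. The weekly-dose summaries in SAP 8.7 are tied to target days and would shift as well.

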13.4 Efficacy Data Handling

Change from baseline to Week X in efficacy endpoints will be calculated from as:

• (Endpoint Value at Week X) – (Endpoint Value at Baseline), where baseline is defined as in Section 13.3.

13.5 Safety Data Handling

For the purposes of AE reporting, three time periods will be defined based upon the onset date of the AE:

- "Pre-treatment AEs" are AEs with onset dates < date of the reported start date of Revcovi in the CLI-06814AA1-01 study.
- "Treatment-emergent AEs" are AEs with onset dates ≥ date of the reported start date of Revcovi in the CLI-06814AA1-01 study and within 30 days following the date of the last dose of Revcovi.
- "Post-treatment AEs" are AEs with onset dates > 30 days after the date of the last dose of Revcovi within study CLI-06814AA1-01.

"Pre-treatment" and "Post-treatment" AEs are considered non-treatment-emergent AEs. For AEs with partially missing onset dates, an onset date is imputed as detailed in Section 14 (Programming Specifications). If an AE has a completely missing onset date, it is counted as a "treatment-emergent" event, unless the stop date is on or before the date of the first dose of study medication.

If relationship to study drug is missing, for analysis purposes it will be assumed to be related to study drug. For AEs which occur more than once within a time period (see above), the AE which is most related to study drug in that time period will be used in the summary of AEs by categories of relationship to study drug. Similarly, the AE with the maximum intensity in that time period will be used in the summary of AEs by categories of severity.

Concomitant medication of interest is any anti-infective medication applied on or after the reported start date of Revcovi in the CLI-06814AA1-01 study, including medication which was initiated prior to the reported start date of Revcovi in the CLI-06814AA1-01 study and continued until or after the reported start date of Revcovi in the CLI-06814AA1-01 study. Imputation rules for partially missing start/stop dates are described in Section 14 (Programming Specifications).

Change from baseline to Week X in safety endpoints will be calculated in the same way as for the efficacy end points.

14. PROGRAMMING SPECIFICATIONS

- The following algorithm should be used to estimate adverse event start dates for which only partial information is known. To conservatively assign start dates as early as possible, the first day on study drug is the reported start date of Revcovi in the CLI-06814AA1-01 study.
 - Missing day and month
 - If the year is the same as the year of first day on drug, then the day and month of the start date of drug will be assigned to the missing fields.
 - If the year is prior to the year of first day on drug, then December 31 will be assigned to the missing fields.
 - If the year is after the year of first day on drug, then January 01 will be assigned to the missing fields.
 - Missing month only
 - Treat day as missing and replace both month and day according to the above procedure.
 - o Missing day only
 - If the month and year are the same as the year and month of first day on drug, then the start date of drug will be assigned to the missing day.
 - If the month and year are before the year and month of first day on drug, then the last day of the month will be assigned to the missing day.
 - If the month and year are after the year and month of first day on drug, then the first day of the month will be assigned to the missing day.

If the resultant imputed start date is after the AE stop date (and the AE stop date is complete), the imputed start date will be reset to the AE stop date.

- Adverse events with partially missing stop dates and the outcome is "Resolved" or "Resolved with sequelae" will have stop dates imputed as follows:
 - *year is missing* date left missing.
 - o month is missing impute 'December'.
 - o *day is missing* impute 'last date of that month'.

- It is assumed that for the start and stop date of Revcovi, at least month and year are known. If day is missing, it will be imputed by the first of the month, if necessary.
- Partially missing start dates for Adagen pre-treatment (Adagen transitioning patients) will be imputed as follows:
 - Day is missing impute 01 of the month
 - Day and month is missing: impute 01July.
- It is assumed that at least month and year is known for the QoL questionnaires, physical examinations, vital signs, and other laboratory data. If the day is missing, day will be imputed by the 15th of the month. If month and/or year is missing, the records will be excluded from all analyses.
- Partially missing dates for the diagnosis of ADA-SCID will be imputed as follows:
 - Year is missing impute with date of birth
 - Month is missing and year is available impute by 01 January. If the imputed date is prior to the date of birth, impute date of birth.
 - Day is missing impute first day of month. If this imputed date is prior to the date of birth, impute date of birth.
- Complete dates for concomitant medications with missing or partially missing start dates will be imputed, if necessary, using the same algorithm described for adverse event onset dates. If the stop date is missing or partially missing and the "ongoing" variable is indicated as 'no', the imputation rule is applied in the following order:
 - *year is missing* the medication will be considered to have been received at all periods after that period determined by the start date. Date is left missing.
 - o month is missing impute 'December'.
 - o *day is missing* impute 'last date of that month'.
- The following algorithm should be used, when necessary, to calculate a start date that is partially missing for medical history:
 - missing day and month January 01 will be assigned to the missing fields.
 - *missing month only* treat day as missing and replace both month and day according to the above procedure.
 - *missing day only* assign first of the month to the missing day.
- Partially missing stop dates will be imputed as:
 - *year is missing*, no imputation. Date left missing.

- *month is missing and year is prior to year of first dose of study medication*impute 'December'.
- month is missing and year the same as the year of the first dose of study medication impute same month as in start date.
- \circ day is missing: impute 'last date of that month'. If this results in a date \geq the date of the first dose of study medication, impute day as the day prior to the first dose of study medication.
- Partial missing death dates will be imputed in the same way as adverse event start dates.
- Date imputations will be applied to the process of assigning study day and should be retained in the analysis datasets, but the data listings should display the original, partially missing dates.
- Adverse event summary tables will only include treatment-emergent AEs. However, listings will include all AEs (i.e., treatment-emergent and non treatment-emergent AEs) with the non treatment-emergent AEs flagged.

